#### 4.3.2 Imputation of Partial Dates

Imputed dates will be used only to assign reported AEs and Medications to the different study Periods: Screening Period, Treatment Period, FU Period; for determining the category for reported Medication as 'PRIOR ONLY', 'PRIOR and CONCOMITANT' or 'CONCOMITANT ONLY' and to determine if an AE is treatment emergent.

Both observed and imputed dates will be included into the analysis datasets. Dates will be displayed in listings with only the information available in the database.

Partial date imputation will follow ADaM conventions. The ADaM approach is to populate the numeric date variables with the imputed date and add a flag variable to the dataset that indicates the level of imputation.

The flag variable can contain the values: blank, 'D', 'M', 'Y' with

blank: indicates that no imputation was done,

D = 'Day': indicates that the day portion of the date is imputed,

M = 'Month': indicates that the month and day portions of the date are imputed,

Y = 'Year': indicates that the entire date (year, month, and day) is imputed.

**Table 4 Partial Date Imputation Rules for AEs and Medications**

Date	Missing Element	Rule
Start Date	day, month, and year	Do not impute completely missing start dates
	day, month only	Set to January 1 st of the year the event started.
	day only	Set start date to the 1 st of the month the event started.
End Date	day, month, and year	No imputation for completely missing end dates; report the event as ongoing if not already documented as 'ongoing'
	day, month only	If the partial end date contains year only, set end date to December 31 st or last study visit, whichever occurs first.
	day only	If the partial end date contains month and year, set the end date to the last day of the end month or last study visit, whichever occurs first.

Thus, AEs will be assumed to be treatment-emergent, unless there is clear evidence to suggest that the AE started prior to treatment.

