### 3.4 Endpoints

#### 3.4.1 Primary

- Incidence of TEAEs, including serious and severe TEAEs, overall and by severity.

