### 4.10.2 Adverse Events

Adverse events will be coded using the MedDRA Version 23.0 or higher.

Treatment-emergent AEs (TEAE) are defined as AEs that either start or worsen in severity on or after the date/time of study drug administration and through the end of study. Partial date imputation was specified in [Section 4.3](#). Imputed dates will only be used for TEAE definition.

An overall summary table of TEAEs will be provided with the number and percentage of patients (incidence) reporting an event along with the total number of events presented for the following categories:

- All TEAEs,
- TEAEs related to Study Drug,
- TEAEs by severity,
- Severity grade 3 and higher TEAEs,
- Severity grade 3 and higher TEAEs related to Study Drug,

- Serious TEAEs,
- Study drug-related serious AEs (SAEs),
- Fatal TEAEs,
- TEAEs leading to study discontinuation,
- SAEs related to COVID-19,
- TEAEs suspected as infusion-related reactions.

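### Table 4 of the SAP can date a post-dose adverse event before dosing and drop it from the primary TEAE count, against the sentence beneath the table

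*SAP*

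**What the plan says.** SAP Table 4 (section 4.3.2) gives these rules for partial start dates:

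- Day missing: the date becomes the 1st "of the month the event started".
- Day and month missing: the date becomes 1 January "of the year the event started".
- Fully missing: no imputation.

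None of these rules mentions the dosing date. Section 4.3.2 says that imputed dates serve, among other things, "to determine if an AE is treatment emergent". Section 4.10.2 agrees: "Imputed dates will only be used for TEAE definition". That section defines TEAEs as "AEs that either start or worsen in severity on or after the date/time of study drug administration", through the end of the study. The primary endpoint in SAP 3.4.1 is "Incidence of TEAEs, including serious and severe TEAEs, overall and by severity".

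Directly below Table 4, presented as following from it, stands: "AEs will be assumed to be treatment-emergent, unless there is clear evidence to suggest that the AE started prior to treatment".

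**The concern.** The sentence does not follow from the table. The first of the month is a default, not evidence of when an event began, yet for any patient dosed after the 1st it lies before dosing. A programmer who codes the table and one who codes the sentence would get different primary results from the same SAP, and the SAP does not say which governs.

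Under the table the error runs one way. The start-date rules only move onset earlier, so a post-dose event can be lost from the TEAE count.

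Whether a pre-dose date could be right depends on the kind of event. Protocol 8.6.3 records AEs only from the start of study drug, so for non-serious events a pre-dose imputed date is usually wrong. Protocol 9.4 collects SAEs from consent, so an SAE with a partial date may truly be pre-dose.

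The table also departs from the SAP's own practice. Section 4.3.1 assumes the worst case for missing severity, and for missing relationship when the event starts on or after dosing. Table 5 foresees that a first-of-month date can precede a reference date and provides for it. Table 4 has no such provision.

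**Working it through.** The documents give no figure for this point, so there is none to reproduce.

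**Inputs**

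- Start-date rules: SAP Table 4.
- TEAE test: imputed start on or after dosing (SAP 4.10.2).
- Study-day formula: SAP 4.2.
- Follow-up of 60 days: SAP 3.1.
- 30 patients randomized 1:1:1, about 10 per arm: SAP 3.1.4.
- Dosing dates: not in the documents, so assumed.

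**Single cases (illustrative dates, day missing)**

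| Dosed | True onset | Imputed start | Study day | TEAE under Table 4? |
|---|---|---|---|---|
| 10 Oct 2020 | 12 Oct 2020 | 1 Oct 2020 | 1 Oct − 10 Oct = −9 | No |
| 10 Oct 2020 | 3 Nov 2020 | 1 Nov 2020 | 22 + 1 = 23 | Yes |
| 1 Oct 2020 | 5 Oct 2020 | 1 Oct 2020 | 0 + 1 = 1 | Yes |

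The loss therefore needs onset in the dosing month and dosing after the 1st. If only the year were known, all three events would be set to 1 January 2020 and none would count. That case is remote in a 60-day study and is not quantified further.

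**Share of day-missing events lost**

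Every dosing date in a window was paired with every onset day:

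share = (pairs with imputed start before dosing) / (all pairs)

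Five dosing windows were assumed: May-Dec 2020; Jun-Oct 2020; Aug-Dec 2020; 8 Apr-9 Dec 2020; 8 Apr 2020-5 Jan 2021. Ranges are across these five.

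| True onset (uniform) | Dated before dosing |
|---|---|
| Days 1-7 | 86.8-87.0% |
| Days 1-14 | 75.3-75.6% |
| Days 1-28 | 52.3-52.8% |
| Days 1-60 | 24.5-24.7% |
| Days 8-14 | 63.7-64.2% |
| Days 15-28 | 29.4-29.9% |
| Days 29-60 | 0.2% |
| Days 31-60 | 0% |
| Days 15-60 | 9.1-9.3% |

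The rows by period matter because later events are more likely to be learned at the Day 28 or Day 60 telephone contact, where a day is more easily forgotten. Let p be the proportion of partial dates with onset after Day 14. For the May-Dec 2020 window:

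overall share = (1 − p) × 75.5% + p × 9.2%

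- p = 0: 75.5%
- p = 0.5: 37.75% + 4.6%, about 42%
- p = 1: 9.2%

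These are upper bounds. They cover only truly post-dose events with the day missing, and they ignore events that later worsen and so still qualify.

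**Effect on the endpoint**

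Event counts fall by one for each lost event. Incidence falls only if the lost event was the patient's only TEAE, or the only one in its severity or seriousness category. Then it falls by 1/10 = 10 percentage points in one arm, or 1/20 = 5 points in ATYR1923 Total.

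**The case against.** The strongest reply is that the sentence under the table already states the intended default. A programmer who follows it keeps these events, so loss arises under only one of two readings. That is true, but the SAP does not rank the two, and sections 4.3.2 and 4.10.2 both point to the imputed date as the deciding one. The contradiction therefore remains.

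The second reply is that the affected set may be tiny or empty. Much of this stands:

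- Protocol 9.3 requires an onset date and time for each AE.
- Protocol 9.4 requires SAEs to be reported within 24 hours of discovery, with the event date, so partly dated SAEs should be rare.
- Inpatients are assessed almost daily in the first week (Protocol 4.1), so the early events, where the shares are largest, are the least likely to lack a day.
- Forms are verified against source (Protocol 12.3).

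The percentages therefore describe what happens to a partial date and do not estimate bias in the endpoint.

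The third reply is that the study is unpowered and descriptive, the rule is the same in every arm, and nothing is hidden: all AEs are listed, imputed dates are flagged in the datasets, and "Dates will be displayed in listings with only the information available in the database". This limits the harm. It does not correct the tabulated incidence, which is the primary endpoint.

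A single sentence saying that the stated default governs would have the same effect as the change proposed here. It is an acceptable alternative, but it does not show that the table is right.

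**Conclusion.** The concern holds. As written, Table 4 can remove truly post-dose AEs from the primary TEAE count, and it contradicts the sentence beneath it. It should be fixed because it bears on the primary endpoint and errs in one direction only, not because a large effect is expected.

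For a post-dose event with the day missing, the chance of loss runs from at most about 87% for onset in the first week to essentially nil after Day 28. These shares rest on uniform onset and assumed dosing windows, though they barely change across the five windows tried. The number of partial dates is unknown and probably small, so the likely effect on reported incidence is small. With about 10 patients per arm, however, one lost event could move an arm by 10 points in the circumstances shown above.

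**What to change.** Add one row to Table 4, for AE start dates only. If the known month and year match those of dosing (or the known year does, when only the year is recorded), impute the dosing date and treat the event as on or after dosing. The exception is an event for which a recorded end date or other recorded data show pre-dose onset. All other partial dates keep the present rule. Leave the medication rule, which uses the same table, unchanged.

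State the tie rule explicitly. The change puts about 90%, 79%, 56% and 26% of day-missing events (onset in Days 1-7, 1-14, 1-28 and 1-60) on the dosing date with no onset time, while section 4.10.2 compares date and time. Without a tie rule their order is undefined. With it, no truly post-dose, day-missing event is misclassified in any window tried.

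The SAP has already been revised after unblinding, so log this change in the revision history as post-unblinding and report how many AEs it reclassifies.

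The cost is one SAP row, a small programming change and one revision-history entry. TEAE counts may rise slightly, and a truly pre-dose SAE with a partial date could be counted as treatment-emergent.

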**Table 5 Partial Date Imputation Rules for Death and Hospitalization**

Missing Element	Rule
month and/or year	Do not impute.
day only	Set start date to the 1 st of the month. If imputing the first day of the month results in a negative overall survival time, the patient will be censored for overall survival at the reference date.

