### 4.2 General Presentation Considerations

**Baseline:** the last available pre-treatment assessment, unless otherwise specify. All assessments should have time collected. If time is not collected and date of assessment is the same as study drug administration date then assessment will be assumed to be collected prior to treatment unless schedule of assessments and protocol indicate planned collection is always after dosing.

For baseline of oxygen use, total oxygen use in 24 hours before drug administration date.

**Day-of-Discharge (DoD):** day when patient is discharged from the hospital.

**Date of discharge:** date patient is discharged from the hospital.

**Early Termination (ET):** day when patient withdraws from the study before completion.

**End-of-Study (EOS):** the EOS assessment is at Day 60 for patients who complete the study.

**End of study date:** date of EOS assessment (Day 60) if patient completes the study or date of early withdrawal if patient discontinues early, or date of death.

**Study Day:** <Assessment Date> - study drug administration date + 1 if <Assessment Date> is on or after study drug administration date. <Assessment Date> - study drug administration date, if <Assessment Date> is before study drug administration date.

Durations are generally calculated as the stop date - start date +1, if not otherwise stated.

For elapsed time (eg, time since the initial diagnosis) is calculated as reference date - event date.

If more than one laboratory value is available for a given study day, the last valid observation will be used in summaries, unless otherwise stated. If it is not possible to determine which is the last measurement due to missing times, then the average of all measurements for that study day will be used as the value for that study day. All observations will be presented in listings.

Laboratory data will be presented in standard units.

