#### 4.9.4.1 Secondary Efficacy Analyses

##### Time to hospital discharge

Time to hospital discharge will be calculated as:

discharge date – study drug administration date.

Patients who die in hospital will be censored at death date. Patients still in hospital at EOS will be censored at EOS visit.

For imputation of partial missing dates for death or discharge from hospitalization see [Section 4.3.2](#).

Additionally, time to hospital discharge will be analyzed using an adapted derivation: discharge date – randomization date. The same rules for handling of hospitalized or discontinued patients and partial missing data applies as mentioned above. Related output will be noted as sensitivity analysis.

Time to hospital discharge will be analyzed based on mITT and EE Set. Sensitivity analysis for time to hospital discharge will be analyzed based on mITT only.

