Number and percentage of patients who died will be summarized by day 14, 28 and 60 by treatment group. If the total number  $\leq 3$ , only listing will be presented.

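### SAP Table 5 can date a discharge before dosing or up to 30 days early when the day is missing, and its own section restricts imputed dates to adverse events and medications

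*SAP*

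**What the plan says.** SAP Section 4.3.2, Table 5, covers death and hospitalization dates. If the month or year is missing, nothing is imputed. If only the day is missing, the date becomes the first of that month. One exception follows: "If imputing the first day of the month results in a negative overall survival time", then "the patient will be censored for overall survival at the reference date". The table does not define the reference date and sets no lower or upper bound on the imputed date.

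Section 4.9.4.1 brings discharge under this rule. Under time to hospital discharge it states: "For imputation of partial missing dates for death or discharge from hospitalization see" Section 4.3.2. The endpoint itself is "discharge date – study drug administration date", and "Patients who die in hospital will be censored at death date".

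The opening of Section 4.3.2 points the other way: "Imputed dates will be used only to assign reported AEs and Medications to the different study Periods", to classify medications as prior or concomitant, and to decide whether an adverse event is treatment-emergent. Death and discharge are not on that list.

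Mortality has no time-to-event analysis. The SAP plans that "Number and percentage of patients who died will be summarized by day 14, 28 and 60 by treatment group". For a patient who does not complete, Section 4.2 sets the end of study date as "date of early withdrawal if patient discontinues early, or date of death".

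**The concern.** The first of the month is the earliest day the event could have happened. For an event in the dosing month it is usually a day on which it could not have happened, because every patient is an inpatient at dosing. The rule can thus place a discharge before dosing, or before days on which the patient was recorded in hospital. The only negative-time provision concerns overall survival, so the programmer has no instruction for a negative time to discharge.

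The discharge date reaches more than one endpoint. Discharge is an event in time to recovery and time to improvement, and it counts toward recovery by Day 14 and Day 28. Recovery and improvement take whichever comes first, so a discharge imputed too early overrides a correctly dated WHO score. The error always runs toward faster discharge and recovery.

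The SAP also gives two answers on whether an imputed discharge date may be used at all. Two programmers could each follow it and get different results.

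**Working it through.** The SAP gives no expected number of partial dates and no power figure, so there is no plan figure to reproduce. The check is calendar arithmetic.

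**Inputs.** Table 5 rule: first of the month. Time to discharge: discharge date minus dosing date (Section 4.9.4.1). Study Day: date minus dosing date plus 1 (Section 4.2). Sample size: 30 patients, 1:1:1 (Section 3.1.4). Assumption, not in the documents: dosing dates uniform over June to December 2020 (7 months, 214 days).

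**1. Formula.** Let m be the day of the month of dosing, L the length of that month, and k the true number of days from dosing to the event.
- Event in the dosing month (m + k ≤ L): imputed time = 1 − m. This is negative unless m = 1, when it is 0.
- Event in the next month: imputed time = L − m + 1.
- In every case, days too early = the event's true day of the month − 1, so 0 to 30.

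**2. Example, dosed 10 August.**
- Discharged in August, day unknown: imputed time 1 − 10 = −9. The possible range is 0 to 31 − 10 = 21.
- Discharged in September, day unknown: imputed time 31 − 10 + 1 = 22. The possible range is 22 to 21 + 30 = 51.

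**3. How often the time is negative, given a missing day.** In each month the dosing days m = 2 to L − k give a negative time, which is L − k − 1 days. Over the seven months the share is (214 − 7(k + 1))/214.

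| Days from dosing to event (k) | Share of dosing dates with negative time |
|---|---|
| 5 | 172/214 = 80% |
| 7 | 158/214 = 74% |
| 14 | 109/214 = 51% |
| 21 | 60/214 = 28% |
| 28 | 11/214 = 5% |
| 35 | 0 (no month is that long) |

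Using all of 2020 instead changes these shares by at most 0.2 percentage points.

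For events spread evenly over 1 to 28 days after dosing, enumeration puts 53% in the dosing month and 49% at a negative time; the gap is dosing on the 1st. The mean shift over all these events is 14.8 days. Among those falling in the month after dosing it is 9.0 days, because within 28 days the event can be no later than the 28th of that month (at most 27 days early).

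**4. Deaths.** Table 5 does not take a death out of the mortality counts, but it can change the window.
- Dosed 20 August, died 10 September: true time 21 (Study Day 22). Imputed date 1 September: time 12 (Study Day 13), so the death is counted by Day 14.
- By enumeration, a death 21 days after dosing is dated within Day 14 for 74% of dosing dates. This includes the 28% with a negative time.
- A death 35 days after dosing is dated within Day 28 for 74% of dosing dates.

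An early death date also shifts the censoring time of an in-hospital death in time to discharge. Because the end of study date can be the death date, it can do the same in endpoints censored at end of study. Those censoring times can also be negative.

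**5. The texts side by side.** The opening of Section 4.3.2 confines imputed dates to adverse events and medications. Table 5, in the same section, imputes death and hospitalization dates. Section 4.9.4.1 refers to that section for use in time to discharge. If the opening sentence governs, Table 5 has no use. If the cross-reference governs, the opening sentence is wrong.

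**6. Size per patient.** 30/3 = 10 per arm, so one misdated patient can move a proportion by 1/10 = 10 percentage points.

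**The case against.** The strongest reply is that the rule may never be used. Protocol Section 8.3.1 requires the date and time of discharge in the eCRF, and discharge assessments are done on the day of discharge. A discharge with month and year known but the day missing should be rare, and the documents report none. This stands, and it limits the point to a minor one.

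The rule is also the same in every arm of a double-blind trial, so no bias between arms is shown. That stands too. What remains is an error in one direction, toward earlier events, and an outcome that can be impossible.

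A reader might infer from the censoring sentence that a known death becomes a non-event. The documents do not support that. The censoring applies only to overall survival, which the SAP never analyses. Mortality is a count of deaths by Days 14, 28 and 60, and in-hospital deaths are censored in time to discharge by design. A death found after discharge cannot change time to discharge, because that event has already happened. Nor can one say that such a patient is censored at time zero, since the reference date is undefined.

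Finally, any replacement that uses the earliest admissible date still leans early. That is true, but such a date is at least consistent with the patient's record.

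**Conclusion.** The point holds as a minor defect. If Table 5 governs discharge, as Section 4.9.4.1 says, a day-missing discharge in the dosing month gets a negative time (zero if dosed on the 1st) with no rule to handle it. One in a later month is dated 0 to 30 days early. Time to discharge, time to recovery, recovery by Day 14 and Day 28, and time to improvement all take that date. For deaths the effect is narrower: a possible move into an earlier Day 14 or Day 28 count, or a wrong or negative censoring time. The contradiction inside Section 4.3.2 holds whether or not any date is partial.

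The percentages rest on the assumed uniform dosing dates and apply only when a day is missing. The number of such patients is not given and may be zero.

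**What to change.** - In Table 5, when only the day is missing, impute the later of the first of the month and the last date the patient is documented in hospital (for discharge) or alive (for death). The date must never precede dosing and is capped at the end of the month.
- Keep a known death as a death, and delete the overall-survival sentence.
- Amend the opening of Section 4.3.2 so that it allows imputed death and discharge dates in the efficacy and mortality derivations.
- Report the number of partial death and discharge dates by arm. If there are none, one sentence in the clinical study report closes the point.

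The text change is a few lines. The cost is procedural: the SAP revision history already records versions 2.0 and 3.0 as post-unblinding modifications, so this would be a further one. It must be labelled as such, in line with SAP Section 3.2, and it may affect few patients or none.

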#### 4.4 Software

All report outputs will be produced using SAS® version 9.3 or a later version in a secure and validated environment.

#### 4.5 Analysis Sets

**All Screened** consists of all subjects who provide written informed consent.

**Randomized Set** comprises all patients randomized regardless of whether they received study treatment. Patients will be summarized and analyzed ‘as randomized,’ ie, by randomized treatment group.

**Modified Intention-to-Treat Set (mITT Set)** comprises all patients randomized who have received any amount of study drug. Patients will be summarized and analyzed ‘as randomized,’ ie, by randomized treatment group.

**Safety Set** is defined as all randomized patients who received any amount of study drug. Patients will be summarized and analyzed ‘as treated,’ ie, by actual treatment group.

**Pharmacokinetic Set (PK Set)** is defined as patients that receive at least one dose of study drug and have at least 1 evaluable post-dose PK sample.

A by-patient listing of analysis set details including patient identifier, inclusion/exclusion flag for each set, and reason for exclusion from each set.

**Efficacy Evaluation Set (EE Set)** comprises all patients randomized and dosed who do not have any major violations or other findings upon medical review that the Sponsor determines might impact the efficacy evaluation.

**Technical Note:** The sponsor will provide a CSV file containing a list of all subjects and a flag if that subject will be included or exclude from EE Set.

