## REVISION HISTORY

Version No.	Effective Date	Summary of Change(s)
1.0	09 Dec 2020	New document
2.0	05 Mar 2021	
Correction of typographic errors
 
Post-unblinding Modifications after sponsor review:
 
 
• New definition and analysis of Time to recovery with WHO scale score <math>\leq 3</math> without supplemental oxygen added, see Section 4.9.4.1
 
• additional baseline categories, see Section 4.7
 
• additional concomitant medication of special interest, see Section 4.8
 
• Grading added for Urinalysis, see Section 6.3
 
• Efficacy Evaluation Analysis Set added, see Section 4.5
 

3.0	24 Mar 2021	
Minor Post-unblinding Modifications after sponsor review:
 
 
• Update Time to recovery with WHO scale score <math>\leq 3</math> without supplemental oxygen
 

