### 4.6.2 Protocol Deviations

All identified protocol deviations throughout the study will be listed prior to database lock. Protocol deviations will be identified and classified into major or minor. Major protocol deviations are defined as those that could have a significant effect on the subject's safety, rights, or welfare and/or on the integrity of the study data.

During the blinded data review meeting (BDRM), the subject's assignment to or exclusion from any analysis set will be discussed in detail. The decisions made during the BDRM will be documented in the BDRM minutes and agreed upon prior to database lock and unblinding for final analysis.

The following summaries will be provided for mITT set:

- all major protocol deviations related to inclusion and exclusion criteria,
- all other major protocol deviations.

A by-subject listings will be provided for all reported protocol deviations.

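### The Efficacy Evaluation Set, logged as a post-unblinding addition, has an open, sponsor-judged exclusion rule that SAP 4.5 does not tie to the blinded review in SAP 4.6.2

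*SAP*

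**What the plan says.** **Definition.** SAP 4.5 starts from randomized, dosed patients and removes those with major violations or "other findings upon medical review that the Sponsor determines might impact the efficacy evaluation". The technical note gives the mechanism: "The sponsor will provide a CSV file containing a list of all subjects and a flag" for inclusion or exclusion. Section 4.5 does not list the qualifying findings, date the flags or say that the person flagging must be blinded.

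**Origin.** The SAP revision history, version 2.0 (05 Mar 2021), has the entry "Efficacy Evaluation Analysis Set added" under the heading "Post-unblinding Modifications after sponsor review". Version 1.0 is dated 09 Dec 2020.

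**General rule.** SAP 4.6.2 says that at the blinded data review meeting a patient's assignment to or "exclusion from any analysis set will be discussed in detail", and that the decisions are minuted and "agreed upon prior to database lock and unblinding for final analysis".

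**Interim.** SAP 3.1.5 plans an interim safety analysis reviewed by a sponsor team that knows treatment group.

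**Use.** SAP 4.9.4.1 runs five time-to-event analyses on EE beside mITT: hospital discharge, recovery, recovery without supplemental oxygen, and improvement by at least one and at least two points.

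**The concern.** mITT membership follows a fixed rule: randomized and dosed. EE membership rests partly on a sponsor judgement with no stated limits, for a set that the SAP's own log places after an unblinding. Someone who knows both arm and outcome could, within the wording of 4.5, exclude a patient whose result is inconvenient. The planned listing of exclusion reasons would show a reason, but 4.5 offers no closed rule to test it against.

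With 30 patients randomized 1:1:1, a single exclusion carries weight. The EE hazard ratios would appear beside the mITT ones and could be read as equally well planned.

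**Working it through.** The plan gives no figure for the EE Set to reproduce, so the check has two parts: a reading of the text and an illustration of size.

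**1. The passages side by side**

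| Question | SAP 4.5 (EE Set) | SAP 4.6.2 (any set) |
|---|---|---|
| Grounds for exclusion | Major violations, or findings the sponsor judges relevant | Decided at the review meeting; major deviations are defined |
| Who decides | Sponsor, by flag file | Blinded review meeting, with minutes |
| When | Not stated | Before database lock and final unblinding |
| Blinded | Not stated | Yes |

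Neither section refers to the other on EE flags. The log's word unblinding has two possible readings.

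- *Final unblinding.* A set created afterwards cannot have had its membership agreed beforehand, so the EE Set cannot have met 4.6.2.
- *Interim unblinding.* 4.6.2 need not be breached. But a sponsor team already knew treatment group, and 4.5 does not keep that team from setting flags.

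On either reading, 4.5 needs reconciling with 4.6.2 and the log.

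**2. How far a few exclusions can move a result**

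Inputs from the documents: 30 patients in three arms, so 30/3 = 10 per arm; follow-up to Day 60; hazard ratios from a single Cox model (SAP 4.9.4). One exclusion is 1/10 = 10% of an arm; two are 2/10 = 20%.

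Assumptions, because the documents do not give these:

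- No treatment effect.
- Exponential times with median 4, 6, 8 or 12 days, plus a Weibull with shape 1.5 and median 6 days.
- Times rounded up to whole days and censored at Day 60; no deaths or withdrawals.
- Efron ties. A result is favourable when z = log(HR)/SE > 1.96 (nominal one-sided 2.5%).
- Total v placebo is the equal-weight contrast (b1 + b2)/2 of the two dose effects; the SAP does not state the contrast.

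With R = 5,000 trials per setting, the Monte Carlo standard error is sqrt(p(1-p)/R): sqrt(0.025 x 0.975/5000) = 0.22 points, and sqrt(0.15 x 0.85/5000) = 0.5 points.

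False-favourable rate, three-group Cox model, range over the five time distributions:

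| Patients removed | Total v placebo | One dose v placebo |
|---|---|---|
| None | 2.2-3.0% | 2.8-3.3% |
| 1 or 2 at random | 2.2-3.2% | 2.8-3.4% |
| 1 or 2 slowest, regardless of arm | 2.5-3.2% | 2.9-3.4% |
| Slowest drug patient | 6.1-7.3% | 8.5-9.7% |
| Two slowest drug patients | 11.2-12.9% | 16.3-18.0% |

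A separate run of 1,200 null trials per setting (medians 4 and 12 days) gave 6.3% and 11.6-11.8% for Total, and 9.2-10.2% and 18.0-18.2% for one dose, for one and two removals. The standard error near 10% is sqrt(0.10 x 0.90/1200) = 0.9 points, so the runs agree.

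Over this model and a two-group version, the median hazard ratio moves from about 1.0 to 1.15-1.19 (one removed) or 1.32-1.39 (two removed) for Total. For one dose it moves to 1.28-1.32 or 1.63-1.67.

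**3. Why these rates are not a ceiling**

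Section 4.5 sets no cap on exclusions, and the adverse rows remove only drug patients. In a two-group Cox model, removing the two slowest drug patients gave 9.8-11.0% (20 v 10) and 15.2-16.5% (10 v 10). Choosing the most favourable mix of slow drug and fast placebo patients, up to two, gave 10.9-12.8% and 17.2-18.2%. A greedy log-rank search (assumed median 7 days) with up to three removals reached about 20% and 31%.

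**The case against.** **A blinding rule already exists.** The EE Set is an analysis set, so 4.6.2 covers it, and 4.5 need not repeat the rule. This stands in part. A reader might infer that the SAP never requires blinded assignment; that would be wrong. But the log entry makes it uncertain whether 4.6.2 was, or could have been, applied to this set.

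**Nothing improper is shown.** This stands in full. A reader might infer that the sponsor dropped patients knowing their results. The documents do not say who set the flags, when, or with what knowledge. The log does not establish that the final unblinding is meant either.

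**The stakes are low and safeguards exist.** P-values are exploratory (SAP 4.9.2), mITT is the default efficacy set (4.9.4) and the primary endpoint is safety (3.4.1). The SAP plans exclusion reasons by patient (4.5), counts per set (4.6.1) and deviation listings (4.6.2). These limit the damage but do not supply a rule: a finding that is not a deviation need not appear in the deviation listing. SAP 3.2 requires a post hoc label only for analyses after database lock, and 4.5 adds none.

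**The rates are hypothetical.** This stands. They neither estimate what happened nor bound what could. Inflation requires exclusions that depend on both outcome and arm.

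**One further step is not supported.** A reader might add that the major/minor classification is undated. In 4.6.2 the sentence "Protocol deviations will be identified and classified into major or minor" directly follows "All identified protocol deviations throughout the study will be listed prior to database lock", and the next paragraph fixes set decisions before lock. The natural reading dates both.

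**Conclusion.** The concern holds as a defect in the rule, not as evidence of misuse. Section 4.5 permits exclusions that could depend on arm and outcome, and it must be reconciled with 4.6.2 and the revision history.

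Under the assumptions above, removing one or two slow drug patients takes the false-favourable rate from near nominal to about 6-7% or 11-13% for Total v placebo, and about 8-10% or 16-18% for one dose. More removals, or removing fast placebo patients as well, would raise it further. Random or arm-blind removal does not raise it, which is the reason to ask for blinded flags.

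The effect is confined to the five EE analyses. A reader might infer that the trial's efficacy or safety results as a whole are compromised; mITT and Safety Set membership do not depend on the flags, so those results are unaffected. This should be fixed, but it does not threaten the primary objective.

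**What to change.** 1. In SAP 4.5, delete the open clause on other findings. Limit EE exclusions to major protocol deviations that affect the efficacy data, as classified and documented at the blinded data review before database lock and unblinding. The restriction to efficacy data matters because 4.6.2 also counts deviations touching only safety, rights or welfare as major. State that major violations in 4.5 means the major protocol deviations of 4.6.2, and that the sponsor's file only transfers those decisions.
2. Reconcile 4.5, 4.6.2 and the revision history: state which unblinding is meant, who set the flags, when, and whether they were blinded.
3. If the set or its flags were fixed after final unblinding, or by anyone unblinded at the interim, title every EE output post hoc and say why. Otherwise state that the set was added after the interim with blinded flags.
4. State that efficacy conclusions rest on mITT.

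Showing treatment arm in the planned exclusion listing and adding an entry to SAP Table 1 are optional.

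The cost is SAP wording and table titles; no new data are needed. The downside is that EE membership may differ from the sponsor's current list, with an unknown effect on the EE results.
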